7 STATISTICAL METHODS

7.1 SAMPLE SIZE DETERMINATION

A previous bronchiolitis trial of 615 patients¹⁹ found a standard deviation for HADS scores of 4.1 and a serial correlation of the HADS score between an admission and 7-day assessment that exceeded 0.80 ([name], personal communication, October 18, 2017). To provide as conservative assessment of statistical power, we assume that the serial correlation over 7 days will equal or exceed 0.65 in the present study. We designated a non-inferiority margin on the anxiety portion of the HADS of 2 points, the smallest clinically meaningful change. Based on the non-adherence to recommended follow-up encountered in our pilot study,²² we estimated that up to 33% of patients randomized to as needed follow up would still follow up and that 13% of patients randomized to scheduled follow up would not attend follow up appointments. Hence, the non-inferiority margin for the ITT analysis of all randomized patients was adjusted to be $2 \times (1-0.33-0.13) = 1.08$. We also assumed that the follow-up anxiety assessment would be obtained for at least 90% of subjects. Under these assumptions, a total sample size of 294 patients (147 patients in each group) will provide 80% power with 1-sided α =0.025 for the analysis of covariance planned for the primary analysis to demonstrate non-inferiority of as needed follow up if in fact as needed follow up and scheduled follow up lead to equal levels of anxiety. Because children discharged home with supplemental oxygen are not being randomized and are not being analyzed in the main analysis, these patients are not included in the power calculation.

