1.2 PILOT DATA

To prepare for BeneFIT, we conducted an observational pilot study²² of children hospitalized for bronchiolitis during the winter of 2016-17. All five BeneFIT medical centers (listed in section 3) participated. Among 199 enrolled subjects, a routine follow-up visit was either recommended or scheduled by the primary team in 84% of cases. Two-thirds of patients who completed the study attended a routine follow-up visit, including 87% of those who had a follow up appointment scheduled prior to hospital discharge and 33% of those for whom as needed follow up was recommended.

"Reassurance provided" (70%) and "education provided" (15%) were cited by parents as the most useful aspect of the follow-up visit. Hospital re-visits were uncommon (2%).

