6 STUDY ASSESSMENTS AND PROCEDURES

6.1 STUDY INTERVENTION

Scheduled follow up

At the time of hospital discharge, parents will be instructed to have their child follow up with their PCP within 4 days of discharge regardless of improvement and/or symptom resolution. Research coordinators will verify that the child has a scheduled follow up appointment prior to discharge and will help with scheduling if necessary.

As needed follow up

At the time of hospital discharge, parents will be instructed that the child does not need to automatically follow up with his/her primary care physician. Rather, the child should follow up on an as needed basis: if the child does not improve or if new concerns arise.

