7.2 STATISTICAL ANALYSES

7.2.1 ANALYSIS OF THE PRIMARY AND SECONDARY ENDPOINT(S)

Intent-to-treat analysis for primary outcome

The primary non-inferiority analysis will be an analysis of covariance comparing HADS scores approximately 7 days after discharge between patients randomized to scheduled PCP follow up or as needed PCP follow up, controlling for baseline HADS scores. A 1-sided upper 97.5% confidence bound for the difference in mean HADS score between the intervention and control groups will be constructed, and non-inferiority will be inferred if the upper confidence limit excludes the intent-to-treat non-inferiority (ITT) bound of 1.08 points.

ITT comparisons for secondary outcomes

A log-rank test will be used to compare the time from discharge to the first report of symptom resolution between the randomized treatment groups. Follow-up for symptom resolution will be right-censored at 50 days after discharge or at the time of loss-to-follow-up. Charges will be compared between the two intervention groups using two-part models, given that charge data will likely be semi-continuous. Other secondary outcomes will be compared between the randomized groups using Poisson or negative binomial models with robust standard errors for statistical inference.

Instrumental variable analysis of the effect of the routine follow-up visit

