The primary ITT analyses evaluate the effect of a recommendation for scheduled PCP follow up or as needed follow up, irrespective of whether the PCP visit actually occurs. We will supplement the ITT analyses with an instrumental variable analysis, using randomization as the instrument, which will approximate the average causal effect on parental anxiety of actually receiving routine PCP follow up. The goal of this analysis is to estimate the local average causal effect of the treatment among the subgroup of patients who would attend the PCP visit if randomized to the scheduled follow up group but not if randomized to as needed follow up.²⁶ The validity of instrumental variable analysis depends on an "exclusion" assumption which requires that the randomized intervention affects parental anxiety only through the occurrence or nonoccurrence of the PCP visit and not by other pathways. It also depends on a monotonicity assumption that requires that randomization to the as needed follow up intervention could not cause any subjects to attend a PCP visit when they would not have attended a PCP visit if randomized to the scheduled follow up intervention. Because these assumptions are not fully testable, the instrumental variables analysis will be exploratory.

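### Do the fixed 1.08-point bound and the undefined visit window leave the effect of the follow-up visit itself unsettled?

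*Combined protocol and SAP*

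**What the plan says.** Section 7.1 sets the margin at 2 points and then allows for non-adherence: "we estimated that up to 33% of patients randomized to as needed follow up would still follow up", and 13% of the scheduled arm would not attend. Section 1.2 gives the pilot source. Attendance was "87% of those who had a follow up appointment scheduled prior to hospital discharge". Where a visit was left to the family's judgement, it was "33% of those for whom as needed follow up was recommended". Neither figure has a denominator or interval. "Hence, the non-inferiority margin for the ITT analysis of all randomized patients was adjusted to be" 1.08 points, and section 7.2.1 uses that figure as a fixed rule: "non-inferiority will be inferred if the upper confidence limit excludes the intent-to-treat non-inferiority (ITT) bound of 1.08 points".

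Section 7.2.1 then separates two questions. It describes the intent-to-treat analysis as concerning the recommendation, whether or not a visit takes place. The effect of the visit goes to an instrumental variable (IV) analysis with randomization as the instrument, "which will approximate the average causal effect on parental anxiety of actually receiving routine PCP follow up". The exclusion and monotonicity assumptions are spelled out, and the section ends: "Because these assumptions are not fully testable, the instrumental variables analysis will be exploratory".

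On timing, section 6.1 tells parents in the scheduled arm to have the child "follow up with their PCP within 4 days of discharge". Section 2.1 places the outcome HADS at days 5–9. Section 2.2 collects ambulatory visits until symptoms clear or day 50. Section 6.3 says the reason for each visit, routine or new concern, is documented.

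**The concern.** Scaling 2 points by attendance makes sense only if 2 points is the cost of missing the visit. A reader may therefore take a positive primary result as excluding 2 points per visit. That inference depends on the attendance contrast, which was taken from an observational pilot. The threshold it needs, 1.08/2 = 0.54, is exactly the assumed contrast, so there is no slack.

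The IV analysis would answer the visit question without the attendance guess, but section 7.2.1 does not set its result against 2 points. It also does not say by when a visit must occur to count. A visit after the HADS cannot have influenced it, yet visits are collected for weeks afterwards. Counting late visits would distort the estimated contrast and so the IV estimate. At stake is the reading of the supplementary visit effect, not the primary conclusion.

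**Working it through.** **Inputs.** From section 7.1: SD 4.1, correlation 0.65, 147 per arm, 90% follow-up (132.3 evaluable per arm), one-sided α 0.025, margin 2 points, attendance 87% and 33%. Let D be the difference in attendance between arms.

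**1. The plan's figures.** Margin: 2 × (1 − 0.33 − 0.13) = 2 × 0.54 = 1.08. Residual SD: 4.1 × √(1 − 0.65²) = 3.116. SE of the adjusted difference: 3.116 × √(2/132.3) = 0.383. Power at no difference: Φ(1.08/0.383 − 1.96) = 80.5%. The stated 80% reproduces.

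**2. From the recommendation to the visit.** Under exclusion and monotonicity, and treating D as fixed, visit effect = ITT effect / D. The columns below are:
- A: visit effect corresponding to an ITT limit of exactly 1.08, which is 1.08/D
- B: chance of passing 1.08 if the visit effect is 2, which is Φ((1.08 − 2D)/0.383 − 1.96)
- C: visit-effect limit when the ITT estimate is zero, which is 1.96 × 0.383/D = 0.751/D
- P: power to exclude 2 points with the IV limit when there is no effect, which is Φ(2D/0.383 − 1.96)

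| D | A | B | C | P |
|---|---|---|---|---|
| 0.40 | 2.70 | 11.0% | 1.88 | 55% |
| 0.50 | 2.16 | 4.0% | 1.50 | 74% |
| 0.54 | 2.00 | 2.5% | 1.39 | 80% |
| 0.60 | 1.80 | 1.2% | 1.25 | 88% |
| 0.67 | 1.61 | 0.4% | 1.12 | 94% |

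Column A describes a trial whose limit falls right at 1.08. Any ITT limit below 2D excludes 2 points per visit. At a zero estimate that holds down to D = 0.751/2 = 0.375.

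**3. How far D might stray.** With 147 per arm and the plan's percentages, SE(D) = √((0.87 × 0.13 + 0.33 × 0.67)/147) = 0.048, so an observed D would have a 95% interval of about 0.45 to 0.63. The plan calls 33% an upper figure. At that figure, D = 0.40 needs scheduled attendance of only 73%, although section 6.1 has coordinators confirm the appointment before discharge.

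**4. The visit window.** The documents give no attendance before the HADS, so this step rests on assumed values. Suppose 33% is as needed attendance by day 50, scheduled attendance is 87% and complete before the HADS, and a is as needed attendance before the HADS. Counting all visits multiplies the IV estimate by (0.87 − a)/0.54. A true 2.0 becomes:
- a = 0.20: 2.0 × 0.67/0.54 = 2.48
- a = 0.25: 2.0 × 0.62/0.54 = 2.30
- a = 0.33: 2.00

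The interval widens by the same factor, so the error is towards caution. The reverse needs late visits concentrated in the scheduled arm. For example, 80% before the HADS and 87% later, with 33% throughout in the other arm, gives 2.0 × 0.47/0.54 = 1.74.

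**5. The two worries together.** With a = 0.20, the contrast that matters for the HADS is 0.87 − 0.20 = 0.67, not 0.54. Column B is then 0.4%. In that scenario a serious window problem leaves the fixed bound with room to spare. The two concerns cannot both apply at full size.

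**The case for a change.** The strongest case is that an exploratory estimate still needs a defined exposure. A window chosen after seeing the data is an avoidable freedom. Setting the IV limit against 2 points would also keep its error near 2.5% at any D, because it amounts to asking whether the ITT limit lies below 2D. It would cost a few sentences.

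Part of this stands. Section 7.2.1 gives neither a cut-off nor a reference value, and it does not say whether new-concern visits count. An ITT limit between 2D and 1.08 would not exclude 2 points per visit when D is below 0.54.

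It does not carry further, because nothing the trial decides would change. The section states an estimation goal, not a test. The 2 points are already in section 7.1 for anyone reading the interval. A failed comparison would not overturn the primary result. The 4–11% figures belong to an inference that the plan assigns to a different analysis. Making the comparison more formal would also lend weight to an analysis whose assumptions are doubtful here: section 6.2 encourages PCPs to telephone families, which could affect anxiety without a visit.

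**Conclusion.** No change follows. The primary question concerns the recommendation, and for that 1.08 is stricter than 2 whatever the attendance. The ANCOVA, the bound and the sample size are unaffected. The dependence on D ≥ 0.54 is real but narrow: it affects only a limit between 2D and 1.08, and only for a reading that section 7.2.1 does not claim.

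The missing visit window is a gap that analysts can fill sensibly. The scheduled visit is due within 4 days, the outcome is taken at days 5–9, and visit reasons are recorded. An analyst estimating an effect on that HADS would count visits before it and report attendance by arm.

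The figures rest on the plan's SD, correlation and follow-up rate, on D treated as fixed, and on the exclusion and monotonicity assumptions. The window sizes also rest on attendance before the HADS, which the documents do not give.

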7.2 STATISTICAL ANALYSES

7.2.1 ANALYSIS OF THE PRIMARY AND SECONDARY ENDPOINT(S)

Intent-to-treat analysis for primary outcome

The primary non-inferiority analysis will be an analysis of covariance comparing HADS scores approximately 7 days after discharge between patients randomized to scheduled PCP follow up or as needed PCP follow up, controlling for baseline HADS scores. A 1-sided upper 97.5% confidence bound for the difference in mean HADS score between the intervention and control groups will be constructed, and non-inferiority will be inferred if the upper confidence limit excludes the intent-to-treat non-inferiority (ITT) bound of 1.08 points.

ITT comparisons for secondary outcomes

A log-rank test will be used to compare the time from discharge to the first report of symptom resolution between the randomized treatment groups. Follow-up for symptom resolution will be right-censored at 50 days after discharge or at the time of loss-to-follow-up. Charges will be compared between the two intervention groups using two-part models, given that charge data will likely be semi-continuous. Other secondary outcomes will be compared between the randomized groups using Poisson or negative binomial models with robust standard errors for statistical inference.

Instrumental variable analysis of the effect of the routine follow-up visit

The primary ITT analyses evaluate the effect of a recommendation for scheduled PCP follow up or as needed follow up, irrespective of whether the PCP visit actually occurs. We will supplement the ITT analyses with an instrumental variable analysis, using randomization as the instrument, which will approximate the average causal effect on parental anxiety of actually receiving routine PCP follow up. The goal of this analysis is to estimate the local average causal effect of the treatment among the subgroup of patients who would attend the PCP visit if randomized to the scheduled follow up group but not if randomized to as needed follow up.²⁶ The validity of instrumental variable analysis depends on an "exclusion" assumption which requires that the randomized intervention affects parental anxiety only through the occurrence or nonoccurrence of the PCP visit and not by other pathways. It also depends on a monotonicity assumption that requires that randomization to the as needed follow up intervention could not cause any subjects to attend a PCP visit when they would not have attended a PCP visit if randomized to the scheduled follow up intervention. Because these assumptions are not fully testable, the instrumental variables analysis will be exploratory.

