2.2 SECONDARY OBJECTIVES AND ENDPOINTS

Secondary objectives of the study include determining whether as needed PCP follow-up, compared to scheduled PCP follow-up:

- Does not adversely impact satisfaction with care?
- Does not adversely impact the relationship between the child's primary caregiver and the child's PCP?
- Does not prolong time to resolution of symptoms?
- Does not increase risk of hospital re-admissions and emergency department visits?
- Results in a fewer number of post-discharge ambulatory visits?
- Results in less ambulatory testing (pulse oximetry, chest x-ray) and fewer prescriptions (albuterol, antibiotics, steroids)?
- Results in fewer missed days from daycare and work?
- Results in lower medical costs?

Secondary Outcomes

Measured by parent report via weekly research coordinator phone calls, until symptoms resolved or 50 days after discharge, whichever occurs first:

- Time from hospital discharge to cough resolution
- Time from hospital discharge to child reported back to normal

Measured by parent report via weekly research coordinator phone calls, until symptoms resolved or 50 days after discharge, whichever occurs first:

- Number of hospital re-admissions and emergency visits
- Number of ambulatory visits
- Number of missed daycare and work days
- Ambulatory prescriptions (albuterol, antibiotics, steroids)
- Ambulatory testing (i.e. pulse oximetry, chest x-ray)- only measured at first ambulatory visit

Measured by parent report via research coordinator phone call at 1 month from discharge:

- Relationship with PCP measured by the Patient-Doctor Depth-of-Relationship Scale²⁴
- Satisfaction with care, measured by applicable questions from the Patient Satisfaction Questionnaire Short Form (PSQ-18)²⁵
- Immunizations received

Measured among patients cared for at Intermountain clinics and those who have Select Health insurance:

- Total charges for ambulatory medical care from discharge until:
 - 14 days after discharge
 - symptom resolution

Measured at the time of discharge and during the first follow up phone call:

• Perceptions about pulse oximetry monitoring

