6.3 MEASURES TO MINIMIZE BIAS: RANDOMIZATION AND BLINDING

Randomization

After consent and enrollment, a research coordinator at the site will obtain a site-specific computergenerated randomization assignment for each patient. Patients will be randomized with equal (1:1) allocation to either the scheduled PCP follow up group or to the as-needed PCP follow up group, using randomly permuted blocks of random sizes. Randomization sequences will be stratified by site but not by any additional baseline factors. The research coordinator will inform the patient's family, inpatient medical team, and PCP of the patient's assignment.

Blinding

BeneFIT will be an unblinded trial because it will not be feasible to blind parents or research coordinators to intervention assignment, as the reason for any follow-up visit (i.e. routine vs new concern) that occurs needs to be documented. However, investigators responsible for analyses will be blinded to individual patient intervention assignments.

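### Randomization is stratified by site but the primary ANCOVA leaves site out, so the non-inferiority bound may be slightly wider than the design warrants

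*Combined protocol and SAP*

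**What the plan says.** On allocation, section 6.3 states: "Randomization sequences will be stratified by site but not by any additional baseline factors". Assignment is 1:1, "using randomly permuted blocks of random sizes". Section 3 lists five hospitals, two tertiary and three community.

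On analysis, section 7.2.1 specifies an ANCOVA of HADS anxiety at about 7 days, comparing scheduled with "as needed PCP follow up, controlling for baseline HADS scores". Non-inferiority is decided only by whether the one-sided upper 97.5% confidence limit lies below 1.08 points. For symptom resolution, the same section says: "A log-rank test will be used to compare the time from discharge to the first report of symptom resolution between the randomized treatment groups". No stratification of that test is mentioned.

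Section 7.1 sizes the trial "for the analysis of covariance planned for the primary analysis", using an SD of 4.1, a baseline to day-7 correlation of 0.65, 90% follow-up and a true difference of zero. It does not mention site. No section adds a site term or explains its absence.

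**The concern.** Blocking within site keeps the arms nearly balanced at every hospital. Any difference between hospitals in day-7 anxiety then largely cancels from the treatment comparison, and the true sampling variance of the estimated difference falls. An ANCOVA without site does not recognise this: it counts the between-site variation as residual noise and reports a standard error suited to unstratified allocation.

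The mismatch errs on the safe side. A claim of non-inferiority made under the written plan would stand. What is at stake is a bound somewhat wider than it need be, in a trial planned at about 80% power where that bound alone decides the result. The covariate set also has to be fixed in advance, because adding site after seeing a bound close to 1.08 would be open to challenge.

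A site effect is plausible but not shown. The hospitals differ in type, and coordinators read the HADS aloud to parents. Baseline adjustment may absorb some or all of this. The unstratified log-rank test has the same mismatch with the design.

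**Working it through.** **Inputs from section 7.1.** SD 4.1; correlation 0.65; ITT margin 2 × (1 − 0.33 − 0.13) = 1.08; one-sided α 0.025; power 80%; true difference 0; follow-up 90%; 147 per arm.

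**Step 1: reproduce the planned sample size.**
- Residual SD after baseline adjustment = 4.1 × √(1 − 0.65²) = 3.116.
- Evaluable per arm, normal approximation = 2 × (1.96 + 0.8416)² × 3.116² / 1.08² = 130.7, rounded up to 131.
- The noncentral-t calculation needs 132. Then 132 / 0.9 = 146.7, which gives 147 per arm and 294 in total.

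The stated figure is reproduced, so the trial was sized for the baseline-only ANCOVA and that power is met.

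**Step 2: standard error under the plan.** With 132 analysed per arm, SE = 3.116 × √(2/132) = 0.3835. The upper bound lies 1.96 × 0.3835 = 0.752 above the estimate.

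**Step 3: allow for a site effect.** Let *f* be the share of baseline-adjusted day-7 variance that site explains. The documents give no value, so 0, 2, 5 and 10% are assumptions. They correspond to between-site SDs of 3.116 × √*f* = 0, 0.44, 0.70 and 0.99 HADS points.
- True SE under site-stratified allocation = 0.3835 × √(1 − *f*)
- Excess width without site = 1.96 × (0.3835 − true SE)
- Power without site = Φ((1.08 − 1.96 × 0.3835) / true SE)
- Power with site = Φ(1.08 / true SE − 1.96)
- Type I error without site = Φ(−1.96 / √(1 − *f*))

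| *f* | True SE | Excess width (points) | Power without site | Power with site | Type I error without site |
|---|---|---|---|---|---|
| 0% | 0.3835 | 0 | 80.4% | 80.4% | 0.025 |
| 2% | 0.3797 | 0.008 | 80.6% | 81.2% | 0.024 |
| 5% | 0.3738 | 0.019 | 81.0% | 82.4% | 0.022 |
| 10% | 0.3638 | 0.039 | 81.7% | 84.3% | 0.019 |

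From unrounded values, the power forgone is 0, 0.5, 1.4 and 2.7 percentage points.

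**Step 4: a higher correlation.** Section 7.1 says the earlier trial's correlation exceeded 0.80. At 0.80 the residual SD is 4.1 × 0.6 = 2.46 and the SE is 0.3028. Power without site is 94.6 to 95.5% across the same range of *f*, and 0, 0.2, 0.5 and 0.9 points are forgone. The bound is wider by at most about 0.03 points.

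**Step 5: check by simulation.** Assumed: 264 analysed patients, enrolment of 45/25/12/10/8% over five sites, blocks of 2, 4 or 6, and 20,000 trials per setting. Power without and with site was:
- *f* = 0%: 79.8 and 79.8%
- *f* = 2%: 80.0 and 80.7%
- *f* = 5%: 80.4 and 81.9%
- *f* = 10%: 81.6 and 84.3%

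A separate run of 10,000 trials per setting, with enrolment of 40/30/10/10/10%, gave type I error without site of 0.025, 0.022 and 0.019 at 2, 5 and 10%. With site it was 0.025 to 0.026. Both runs agree with the formulas in direction and size.

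**Step 6: cost of adding site when it predicts nothing.** Residual degrees of freedom fall from 264 − 3 = 261 to 264 − 7 = 257. Noncentral-t power at 132 per arm is 80.1% either way.

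**The case against.** The strongest reply is that nothing planned goes wrong. Type I error is at or below its nominal level, power is about the stated 80% in every scenario, and the effect of site is wholly assumed. The 10% case needs site means to vary with an SD of about 1 point after each parent's own baseline has been adjusted for. That is half the 2 points which section 7.1 treats as the smallest meaningful change, and nothing in the documents supports a site effect of that size. At 2% the bound moves by 0.008 points. At a correlation of 0.80 the loss is under 1 point of power. Stratified allocation also already gives the estimate most of its lower variance, so what is forgone is mainly a correctly sized standard error rather than a better estimate.

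All of this stands, and it limits the weight of the point. It does not remove it, because the omission is clear, its direction is known, and correcting it costs almost nothing even if site turns out not to matter.

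The reply is also fair on secondary outcomes. No gain has been quantified there, and site terms suit some of those models poorly.

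**Conclusion.** The concern holds as a minor point of precision. The plan randomizes by site and does not analyse by it. If site predicts day-7 HADS beyond baseline, the bound is conservative by up to 0.039 points and up to 2.7 percentage points of power are forgone, at a site share of 10% and a correlation of 0.65. At shares of 2 to 5% the figures are 0.008 to 0.019 points and 0.5 to 1.4 percentage points. If site predicts nothing, there is no loss.

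The omission and its direction are certain. The size rests on assumed site shares and on treating the five hospitals as the strata. The sample size, the estimate and the validity of a non-inferiority claim are not affected. No magnitude is claimed for the log-rank test or the other secondary analyses.

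**What to change.** In section 7.2.1, define the primary ANCOVA as day-7 HADS on randomized group, baseline HADS and site as a fixed effect, with a rule set in advance for pooling very small sites. Stratify the log-rank test by site.

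For the count and charge models, include site only where event numbers and site coverage allow, and say in advance where it will be dropped or sites pooled. Two cases need this. Hospital re-visits were 2% in the pilot, so about 0.02 × 294 ≈ 6 events can be expected. The charge outcomes are restricted: "Measured among patients cared for at Intermountain clinics and those who have Select Health insurance".

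The cost is one sentence for the ANCOVA and log-rank test and a short rule for sparse outcomes. No new data are needed, the sample size does not change, and at most 4 of about 260 residual degrees of freedom are used. The change should be made before outcome data are seen by arm.

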- •Obtain demographics and relevant medical history
- •After consent and eligibility verification, but before randomization, parent or legal guardian will complete anxiety portion of HADS

Randomization Day of discharge (patients discharged on oxygen will not be randomized)

- •Coordinator will obtain patient randomization assignment
- •Coordinator will notify child's PCP of child's enrollment in study and randomization assignment
- •Scheduled follow up: Family instructed to follow-up with PCP (appointment made prior to discharge)
- •As needed follow up: Family will be instructed to follow-up with PCP on as needed basis

7 day phone call F	Follow-up assessments of study endpoints
--------------------	--

• Parent will complete anxiety portion of the Hospital Anxiety and Deptression Scale (HADS)

• Parent assessment for secondary outcomes collected via phone interview (see script)

Subsequent weekly phone calls Follow-up assessment of study endpoints

• Parent will be contacted weekly to collect secondary endpoint data until symptom resolution or 50 days after discharge whichever comes first (see script)

1 month follow-up

Follow-up Telephone Call

• Patient-Doctor Depth-of-Relationship Scale will be administered

• Participant considered off study at this timepoint or when final weekly phone call occurs (if needed beyond 4 weeks)

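### Section 2.2 asks whether as needed follow-up leaves symptom duration no longer, but the only planned analysis is a log-rank test with no estimate, interval or margin, which cannot support that answer

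*Combined protocol and SAP*

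**What the plan says.** Section 2.2 lists secondary objectives as questions about as needed compared with scheduled follow-up. One is whether as needed follow-up "Does not prolong time to resolution of symptoms". Two endpoints serve it: "Time from hospital discharge to cough resolution" and "Time from hospital discharge to child reported back to normal".

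For the analysis, section 7.2.1 says: "A log-rank test will be used to compare the time from discharge to the first report of symptom resolution between the randomized treatment groups", and then: "Follow-up for symptom resolution will be right-censored at 50 days after discharge or at the time of loss-to-follow-up". It says nothing more on this objective. There is no hazard ratio, difference in days, confidence interval, margin, significance level or rule for answering the question. Table 1 in section 6.2 sets the data collection: "Parent will be contacted weekly to collect secondary endpoint data until symptom resolution or 50 days after discharge whichever comes first".

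The same section handles the primary outcome differently. HADS anxiety is judged by a one-sided upper 97.5% confidence bound against 1.08 points. The instrumental variable analysis also concerns parental anxiety only, so neither rule reaches symptom duration.

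**The concern.** The objective is a no-harm question, and the test answers another one. A log-rank test can give evidence that two recovery curves differ. When it does not reject, the arms may be alike, or there may be a delay that the trial was too small to detect. Fewer children or more families lost make non-rejection more likely, so non-rejection cannot count as evidence that recovery is not slower.

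The endpoint matters. Section 1.1 names faster disease resolution through changes in treatment as one possible benefit of a follow-up visit, so slower recovery is a route by which omitting the visit could harm the child. Without an estimate and interval, readers cannot see how long a delay the data leave open.

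**Working it through.** **The plan's own figure.** Section 7.1 states that "a total sample size of 294 patients (147 patients in each group) will provide 80% power with 1-sided" α = 0.025 for the HADS analysis of covariance.

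- Adjusted SD = 4.1 × √(1 − 0.65²) = 3.116.
- n per group = 2 × (1.960 + 0.842)² × 3.116² / 1.08² ≈ 131. Divided by 0.90 this is 146 per group, 292 in total, against 294 stated.
- Power at 147 × 0.90 per group is 80.5%.

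The primary sample size reproduces. The documents give no corresponding calculation for symptom resolution.

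**What each result could show.** A significant log-rank test with slower recovery under as needed follow-up would answer the question unfavourably. A significant test with faster recovery would be a superiority finding, which is more than the objective asks. If the arms look similar, which is the result the objective is written for, the test is non-significant and the plan offers nothing further to interpret it with.

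**Illustrative size.** The inputs below are assumptions, because the documents state none of them for this endpoint:

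- events d = 294 × 0.90 ≈ 264. The 90% is stated only for the 7-day HADS, and the figure takes every followed child as resolving by day 50;
- two-sided alpha 0.05;
- proportional hazards and 1:1 allocation.

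Expected log-rank statistic: z = −ln(HR) × √d / 2, with √264 / 2 = 8.124. Probability of a non-significant result = Φ(1.96 − z) − Φ(−1.96 − z).

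- HR 0.80 (times 1/0.80 = 1.25 times as long if the hazard is constant): z = 0.2231 × 8.124 = 1.813, giving 56%.
- HR 0.75 (1/0.75 = 1.33 times as long): z = 0.2877 × 8.124 = 2.337, giving 35%.

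Approximate 95% confidence limits are the observed HR × exp(±1.96 × 2/√264) = HR × exp(±0.241).

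- Observed HR 1.0: lower limit 0.79.
- Observed HR 0.80: 0.63 to 1.02, which is non-significant although a large delay remains possible.

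**Range over the assumptions.**

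| Change | Non-significant at HR 0.80 | Non-significant at HR 0.75 |
|---|---|---|
| 211 events (80% of 264) | 63% | 45% |
| 294 events (every randomized child) | 52% | 31% |
| One-sided alpha 0.05, 265 events | 43% | 24% |

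- Simulated trials (147 per group, 10% loss, censoring at 50 days, assumed control medians of 7, 10 and 14 days, daily or weekly recording) had power of 42% to 48% at HR 0.80 and 62% to 66% at HR 0.75. Weekly recording does not change the picture.
- If times are 25% longer but the hazard is not constant (Weibull, 265 events), the non-significant share is 69% at shape 0.8, 41% at shape 1.2 and 22% at shape 1.5.
- With 265 events, 80% power is reached only at an HR of about 0.71 or lower. For 80% power, HR 0.80 needs 631 events and HR 0.75 needs 380. Both exceed the 294 children randomized.

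**The case against.** The strongest reply is that the plan does not draw the inference at issue. Section 7.2.1 says only that times will be compared. Non-inferiority language is confined to the primary outcome, and no confirmatory status is claimed for secondary outcomes. A reader might infer that a non-significant P value will be reported as showing no prolongation, but the documents do not say so. A short plan that names no hazard ratio also does not forbid reporting one. This stands. What remains is that the plan poses the question and names no analysis that could answer it favourably when the arms are similar.

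A reader might also infer that recovery 25% slower would be missed in more than half of trials. The documents do not support this as a general statement. It holds for times 25% longer with a constant hazard at two-sided 0.05. It fails if slower means a 25% lower resolution rate (HR 0.75), if the test is one-sided at 0.05, or if the hazard of resolution rises moderately with time.

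Non-adherence bears on both sides. Section 7.1 allows for 33% and 13%, leaving a contrast of 1 − 0.33 − 0.13 = 0.54. Suppose, as a rough approximation, that this scales the log hazard ratio. An intention-to-treat HR of 0.80 then implies that missing the visit lengthens recovery by exp(0.223/0.54) − 1 ≈ 51%, which is a large effect for an illness that section 1.1 calls self-limited. Conversely, if missing the visit gave HR 0.80, the intention-to-treat HR would be about 0.89 and even harder to detect.

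Finally, other no-harm items in section 2.2 are also paired with difference testing, so one general sentence could cover part of the remedy. That does not remove the gap here, where the effect measure is a time-to-event one.

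**Conclusion.** The concern holds as a mismatch between objective and analysis. A log-rank test without an estimate, interval or margin cannot support a conclusion that recovery is not prolonged. This rests on sections 2.2 and 7.2.1 alone and on none of the assumed figures.

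The percentages only illustrate its size. Under the base assumptions they are about 56% non-significant at HR 0.80 and 35% at HR 0.75, with a lower limit of about 0.79 at an observed HR of 1.0. They move with the event count, alpha, sidedness and shape of the hazard, none of which the documents fix for this endpoint.

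Nor should the point be read as a fault in the sample size. The endpoint is secondary, and the primary calculation reproduces and is unaffected. The change should be made, but the trial's main conclusion does not depend on it.

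**What to change.** In section 7.2.1, for each of the two resolution endpoints (cough resolution and child back to normal):

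- add the hazard ratio for resolution, as needed versus scheduled, and the difference in median or restricted mean days, each with a two-sided 95% confidence interval;
- keep the log-rank test as a test for difference only;
- state that a non-significant log-rank test will not be read as showing that recovery is not prolonged.

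If the investigators want a formal conclusion of no prolongation, they should fix a margin before analysis and judge it by the confidence limit. The margin needs a clinical justification, not merely a value that the sample can support, and it should take account of non-adherence as the HADS margin does. No specific margin is proposed here.

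The cost is a few sentences and one further model per endpoint on data already collected, with no new patients or calls. The downside is that the result may have to be reported as inconclusive.
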